1.2. Methadone providers

Methadone providers will conduct the study interventions under the clinical supervision of the study master counselors. All methadone providers have been trained on basic addiction medicine and will receive further training to deliver the study interventions. We will conduct in-depth interviews with them before and after the intervention phase.

Randomization and Interventions

An investigator will stratify participants by HIV status and randomize them into two frontline interventions using REDCap, as shown in Figure 1. She will send the allocation results to the site research assistants who will then inform providers at the study clinics. This is an open label study so unblinding does not occur. Participants and their counselors, research assistants and data managers are aware of participants' assignment of intervention. Participants will receive two individual sessions of motivational interviewing with their counselors before they get into the frontline interventions and, in Week 13, before the adaptive strategies start. These sessions would boost participants' motivation for intervention and provide them with greater details of the upcoming intervention activities.

Two frontline interventions (Weeks 1-12)

- High intensity: Participants in this arm receive contingency management with the escalating-and-reset schedule throughout 12 weeks. This schedule means participants receive increasing rewards for consecutive negative UDS but if the streak of negative UDS is broken,

their rewards return to the starting level. The maximal reward value over 12 weeks is \$150 USD, equivalent to the average monthly income of our participants.

- Low intensity: Participants in this arm receive contingency management for the first six weeks with the maximal reward value of \$40 USD. For the last six weeks, they attend weekly group education sessions. The topics of group education include 1) Addiction mechanism, 2) Road to recovery, 3) Coping with triggers, 4) Boredom, 5) Building trust and 6) Relapse prevention.

Participants with four consecutive UDS negative with methamphetamine in weeks 11 and 12 are considered to be responsive to frontline interventions. Others are considered non-responsive. Responders to frontline interventions are placed in the maintenance treatment arm. Non-responders are randomized to either enhanced treatment 1 or 2.

Three adaptive strategies (Weeks 14-25)

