- Maintenance treatment: Participants receive two daily automatic unidirectional scripted SMS reminders plus one weekly self-monitoring assessment message over 12 weeks.
- Enhanced treatment 1: Participants attend 12 weekly Matrix group counseling sessions facilitated by the clinic counselors. Our Matrix intervention has the same structure, albeit it is shorter than the original 24-sessions model.
- Enhanced treatment 2: Participants receive the same Matrix intervention plus contingency management over 12 weeks.

Definition of effectiveness measures

Effectiveness measures will be assessed at 13-, 26- and 49 weeks after the first week of frontline interventions and throughout the interventions. Primary outcomes include: (1) increase in HIV viral suppression for HIV-positive participants at 26- and 49-weeks; (2) reduction in HIV risk behaviors for both HIV-positive and HIV-negative participants at 26- and 49-weeks; and (3) reduction in methamphetamine use at 13-, 26- and 49-weeks measured by UDS (point abstinence) and self-report (continuous abstinence and longest period). Secondary outcomes include: (1) adherence to antiretroviral treatment for HIV-positive participants; 2) frequency of HIV testing for HIV-negative participants; 3) heroin use with UDS; 4) opioid overdose; and, 5) quality of life.

To acquire the primary and secondary outcomes, we will assess for the following:

- HIV viral load test. At baseline, Week 13, Week 26 and Week 49, we send blood samples of HIV-positive participants to laboratories at Bach Mai Hospital in Hanoi and HCMC University of Medicine and Pharmacy Hospital in HCMC for viral load quantification.

- Drug screening. We use an FDA-approved Multi-Drug Rapid Test Panel to detect methamphetamine, opioid, and cannabis in urine twice a week throughout the intervention period and at Week 49.
- Methadone and HIV treatment. We extract methadone and HIV treatment data from participants' medical charts. Variables of interest include length of treatment, treatment regimen, medication dose and treatment adherence.

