necessary; two counselors will run motivational interviewing, group education sessions and Matrix meetings; the nurse will collect urine twice a week and conduct contingency management based on the UDS results. Before the start of the intervention, to ensure the accuracy, integrity and fidelity to the EBIs, all intervention staff at methadone clinics will (1) receive didactic training on the theory behind the approach; (2) evaluate their comprehension of the concepts within and behind the approach; (3) watch a video of a Master Behavioral Counselor conducting intervention sessions and discuss the details of the session, and (4) conduct at least two pilot intervention instances. All intervention sessions, except contingency management, will be audio recorded, transcribed, and coded to ensure intervention fidelity. Intervention staff who have lower levels of intervention integrity or who have significant drift will be provided detailed feedback and supervision until there is parity with other staff.

Sample size determination

Sample sizes were chosen to compare primary outcomes based on first-stage randomization into one of two groups: high intensity or low intensity frontline interventions. Sample size calculations are conducted in PASS 2008 (65) for a two-group comparison of binary outcomes, a power of 80%, a 5% alpha level, and a conservative attrition rate of 20%. Using estimates from our prior work, we anticipate base rates of 80% to 90% for substance use and 60% to 70% for viral suppression. Based on these assumptions and a proposed sample of 200 HIV-positive participants (with 100 participants per group), we can detect randomization group differences of 20% or more for binary outcomes, such as substance use and viral load suppression. We can detect even smaller group differences for substance use outcomes in the proposed sample of 400 HIV-negative participants and the combined sample of HIV-positive and negative participants. If estimated outcome probabilities are similar between first-stage randomization groups at 12 weeks, we will pool 12-week results for even greater power in evaluating second-stage randomization differences.

Table 1. Assessment schedule

Assessments	Baseline	Week 13	Week 26	Week 49
Sociodemographic characteristics	X			X
Drug use history	X		X	X
Current drug use	X		X	X
Amphetamine use behaviors				
Amphetamine Cessation Symptom Assessment (ACSA)				

Tobacco smoking	X		X	X
Alcohol use	X		X	X
AUDIT-C				

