We will use a time-varying mixed-effects model that will be fitted to the participants' common outcome measures over time. The unadjusted model will include indicators of first-stage and second-stage intervention conditions, time of the assessment (baseline, 13-, 26-, and 49-weeks), and intervention indicators-by-time interaction terms. An additional interaction term of the two intervention indicators will be included to account for any interaction effect between the first and the second stage interventions. The adjusted model will include patients' socio-demographic characteristics, drug use history, HIV-serostatus, and location as fixed effects. The mixed-effects models will include a participant-level random effect to account for repeated observations of each participant, as well as a clinic-level random effect to account for the nested nature within the clinics. We will conduct subgroup analyses among HIV-positive and HIV-negative participants. For the HIV-positive subgroup, the specific outcomes of interest include 1) HIV viral load suppression, and 2) adherence to antiretroviral treatment; and specific outcomes for HIV-negative subgroup include 1) frequency of HIV testing and 2) HIV seroconversion. Substance use will be the common outcomes in models including participants of both HIV statuses.

To assess cost-effectiveness

We will calculate Cost Effectiveness Ratios (CER) for each of the intermediate and final outcomes. The CER is in the broadest terms the difference in per capita costs of administering one intervention (C1-C2) relative to a second, divided by the difference in outcomes between the two interventions (O1-O2):

$$CER = \frac{C1 - C2}{O1 - O2}$$

For example, calculating the CER for adding contingency management to Matrix for non-responders would yield a CER equation. In calculating the CER of high vs. low intensity contingency management at the first randomization stage, the entire range of subsequent costs will be included. Costs of delivering the interventions will be derived from clinic records of time and other inputs, as well as incentive payments, thus providing an estimate of CER from the medical system perspective. We will also evaluate CERs from a societal perspective, using a broad definition of costs, including the social costs of incarceration.

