With the cut-off point of ASSIST ≥ 4 and methamphetamine-positive UDS as originally proposed, there were 26 and 52 eligible participants in two pilot clinics in Hanoi and HCMC, respectively (see Table 2). For the pilot implementation, we randomly recruited 42 participants with ASSIST score ≥ 4 or methamphetamine-positive UDS. After the frontline intervention, 16 (38%) participants were non-responders and randomized into adaptive interventions. At least 50% of the original sample must transition to the adaptive phase for sufficient statistical power. Thus, we decided to recruit more participants with severe use of methamphetamine, as evidenced in both ASSIST score ≥ 10 and methamphetamine-positive UDS. Furthermore, to recruit enough participants for the frontline intervention phase, given most other clinics are smaller than the two pilot ones, we decided to use ASSIST score 'OR' UDS instead of 'AND' to increase the pool of potential participants. We kept the criterion of methamphetamine-positive UDS to compensate for participants with lower ASSIST scores due to desirability bias.

Modification to minimize the impacts of the COVID-19 pandemic

Since late April 2021, the COVID-19 epidemic in Vietnam was severe. HCMC applied a strict lockdown from early July 2021 through September 2021. Some methadone clinics were temporarily closed due to confirmed COVID-19 cases among patients, medications were delivered at community-

based healthcare centers. In the clinics that remained open, clinical activities other than medication dispensing ceased to minimize contact between providers and patients. Unlike HCMC, clinical activities in Hanoi continued, albeit at levels lower than pre-pandemic. In addition, methadone clinics in both cities suffered from staff shortages as many staff were deployed to support ongoing COVID-19 prevention and treatment activities. With advice of the study's Scientific Advisory Board, we developed a response plan to potential COVID-19 interruptions to minimize the pandemic's impact (see Figure 2).

For intervention:

- For group education and Matrix sessions, we will conduct small groups of five or fewer people during the surge of the COVID-19 pandemic when the city authorities forbid large meetings. If we cannot conduct group sessions, we will provide individual sessions of the same content to ensure all participants receive interventions.

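### Pooling the frontline arms to compare enhanced treatment 2 with 1 should not hinge on similar 12-week results, and the main second-stage contrast needs to be named

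*Combined protocol and SAP*

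**What the plan says.** Under Randomization and Interventions, participants are first randomised to high or low intensity frontline treatment. Responders go to maintenance. "Non-responders are randomized to either enhanced treatment 1 or 2".

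Under Sample size determination, the trial is sized on the first-stage comparison, with "a power of 80%, a 5% alpha level, and a conservative attrition rate of 20" per cent. That section then adds "If estimated outcome probabilities are similar between first-stage randomization groups at 12 weeks, we will pool 12-week results", and gives the purpose as "for even greater power in evaluating second-stage randomization differences". It does not say how close is similar, on which outcome, or what happens otherwise.

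Under Data analysis (To assess effectiveness), one mixed model carries indicators for both stages. "An additional interaction term of the two intervention indicators will be included to account for any interaction effect" between them. The pooling condition is not mentioned there, and no main enhanced 2 v enhanced 1 contrast is named.

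Under Modification of eligibility criteria: "At least 50% of the original sample must transition to the adaptive phase for sufficient statistical power". No power figure for the second-stage comparison appears anywhere.

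**The concern.** Similarity of the frontline arms at 12 weeks is a statement about the first-stage main effect. Whether the enhanced 2 v enhanced 1 comparison can be combined across frontline arms depends on something else: whether that second-stage effect differs by frontline arm. Two arms can differ widely at 12 weeks and share one second-stage effect, or look alike at 12 weeks and not share it. The condition does not test what it needs to test.

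It also works against the trial's own aim. The sample size targets a 20-point frontline difference. If that difference is found, the arms are not similar, and the stated route to second-stage power closes.

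At stake are power on the second-stage comparison and clarity about the main result. Two analysts, one following the sample-size section and one following the analysis section, could report different main second-stage estimates. Bias and inflated type I error are not at issue.

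**Working it through.** **Inputs from the protocol.** Sample size determination: 5% alpha, 20% attrition, base rates of 80-90% (substance use) and 60-70% (viral suppression), a 20-point difference, and 100 HIV-positive participants per group. Participants: 600 in total. Study schedule: 200 HIV-positive. Modification of eligibility criteria: 50% transition.

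**Assumptions not in the documents.** Two-sided test, 1:1 allocation at both stages, transition equal by HIV status (and by frontline arm unless stated), the same base rates in non-responders, a common second-stage effect, one visit, no clustering.

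**Formula.** Two-group comparison of proportions with n per group, difference d and mean proportion p̄:

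power = Φ{ [d − 1.96·√(2p̄(1−p̄)/n)] / √[(p1(1−p1)+p2(1−p2))/n] }

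**1. Reproduce the plan's figure.** 100 × 0.8 = 80 per group. For 80 v 60: 1.96·√(0.42/80) = 0.1420 and √(0.40/80) = 0.0707, so (0.2 − 0.1420)/0.0707 = 0.820 and power is 79.4%. For 90 v 70 it is 89.3%. The planned 80% is reproduced.

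**2. Second stage, substance use, all participants.**
- Averaged over frontline arms: 600 × 0.5 × 0.8 / 2 = 120 per enhanced arm. For 80 v 60: (0.2 − 0.1160)/0.0577 = 1.456.
- Within one frontline arm: 60 per enhanced arm. For 80 v 60: (0.2 − 0.1640)/0.0816 = 0.441.
- With 40% v 60% transition by frontline arm: 300 × 0.4 × 0.8 / 2 = 48 and 300 × 0.6 × 0.8 / 2 = 72 per enhanced arm.

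| Analysis | n per enhanced arm | 80 v 60 | 90 v 70 |
|---|---|---|---|
| Averaged | 120 | 92.7% | 97.6% |
| One frontline arm, equal transition | 60 | 67.0% | 78.9% |
| Smaller frontline arm (40%) | 48 | 57.2% | 69.3% |
| Larger frontline arm (60%) | 72 | 75.0% | 85.9% |

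With the unequal split, simulation (200,000 runs) of an equally weighted average of the two frontline arms gives 92.0% and 97.5%, so averaging costs almost nothing. At the pilot's 38% transition (seen under the older eligibility criteria) the ranges are 84-93% averaged and 55-67% in one arm.

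**3. Is averaging valid when the frontline arms differ?** Frontline arms were simulated 20 points apart. With no second-stage effect, type I error of the frontline-stratified test is 4.9-5.3%. With a 20-point second-stage effect (90 to 70 in one arm, 70 to 50 in the other, 60 per cell), power is 94.1%.

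**4. How often would the condition fail?** With no margin stated, two readings are tried for substance use, with 600 × 0.8 / 2 = 240 per frontline arm. A true 20-point gap reaches p<0.05 in 99.8% of trials and shows more than 10 points in 99.2%. A true 10-point gap does so in 72% and 49%.

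**5. Viral suppression, HIV-positive participants.** Averaged: 200 × 0.5 × 0.8 / 2 = 40 per enhanced arm, giving 49.7% (60 v 80) and 61.2% (70 v 90). The difference detectable at 80% power is 27.2 and 23.8 points. Within one frontline arm (20 per enhanced arm) power is 27.6% and 34.8%. At 40% v 60% transition it is 23-29% in the smaller arm (16) and 32-41% in the larger (24).

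**The case against.** The strongest reply is that the power loss is measured against an analysis nobody has written down. A reader might infer that the plan prescribes separate analysis by frontline arm and therefore gives up this power. The documents do not support that. The sample-size section states no fallback, and the only analysis specified is the joint model, from which an averaged contrast can be estimated whatever the 12-week results. Pooling might even mean only dropping the frontline term when the arms look alike and keeping it otherwise, in which case little is lost. This stands: the power figures are conditional. The wrong criterion, and the two sections left unreconciled, remain.

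The choice of an averaged contrast is also partly a preference. The Aims compare four adaptive strategies, and enhanced 2 gives contingency management to people who did not respond to either 12 or 6 weeks of it, so effect modification is plausible. This too stands, and is why the frontline-specific effects should be reported alongside.

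Three further inferences should not be pressed:
- The weak power for viral suppression is not caused by the pooling rule, since it persists when the arms are averaged. That outcome is also primary only later: "increase in HIV viral suppression for HIV-positive participants at 26- and 49-weeks".
- The cost-effectiveness text ("calculating the CER for adding contingency management to Matrix for non-responders would yield a CER equation") does not split by frontline arm, but it is an illustration. Its silence does not show that the clinical and economic contrasts conflict.
- Under some codings the enhanced 2 coefficient would be the effect in one frontline arm only, but the protocol states no coding.

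**Conclusion.** The point holds as a flaw in the stated criterion and a gap between two sections. Similar 12-week results are neither needed for a valid combined enhanced 2 v enhanced 1 comparison nor informative about the interaction that bears on combining. For substance use the condition would almost certainly fail if the frontline difference were the one planned for.

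The size is conditional. If failing the condition led to analysis within frontline arms, power for 20 points in substance use would drop from about 93-98% to about 67-79%, or to 57-69% and 75-86% in the smaller and larger arms under 40% v 60% transition. If the averaged contrast is taken from the joint model, nothing need be lost. All figures rest on the single-visit, unclustered assumptions listed above; the planned model uses repeated measures and a clinic random effect, so its power will differ.

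As a separate matter, the promise of greater power is borne out for substance use (93-98% against 79-89% at the plan's 80 per group) but not for viral suppression (50-61%, detectable difference about 24-27 points).

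**What to change.** 1. In Sample size determination, delete the similarity condition. There and in the effectiveness analysis, state: *Enhanced 2 v enhanced 1 will be estimated in all non-responders, adjusted for frontline arm and HIV status and averaged over frontline arms, whatever the 12-week results. The first-by-second-stage interaction and the effect within each frontline arm will be reported with confidence intervals.*
2. Limit the statement about greater second-stage power to substance use. Add that for viral suppression in HIV-positive participants the averaged contrast has about 50-61% power for 20 points (detectable difference about 24-27 points), with the assumptions listed. Cross-refer to this from the 50% transition statement in Modification of eligibility criteria.

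The cost is text in three places. No participants, visits, assays or model terms are added: the joint model already has both stage indicators and their interaction, and its adjusted form already has HIV status. The downside is that the stated second-stage precision for viral suppression becomes less favourable.

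### The only effectiveness model includes the second-stage arm with its coding unstated; coded as three levels it misses the first-stage contrast the trial is sized on, and nothing in the text forms the four adaptive strategies

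*Combined protocol and SAP*

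**What the plan says.** **Design (Randomization and Interventions).** Participants are first randomized to high or low intensity. Response is then judged: "Participants with four consecutive UDS negative with methamphetamine in weeks 11 and 12 are considered to be responsive to frontline interventions". The second stage follows from it: "Responders to frontline interventions are placed in the maintenance treatment arm. Non-responders are randomized to either enhanced treatment 1 or 2". Only Enhanced 1 versus Enhanced 2 is therefore a randomized second-stage comparison.

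**Sample size (Sample size determination).** The trial is sized on the first-stage comparison of high versus low intensity. It claims to detect 20 points or more with 100 HIV-positive participants per group.

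**Outcomes (Definition of effectiveness measures).** Two primary outcomes are assessed only after second-stage assignment: "increase in HIV viral suppression for HIV-positive participants at 26- and 49-weeks" and "reduction in HIV risk behaviors for both HIV-positive and HIV-negative participants at 26- and 49-weeks". Methamphetamine use is primary at weeks 13, 26 and 49.

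**Analysis (Data analysis, To assess effectiveness).** One mixed-effects model is given, with an adjusted version and HIV-status subgroups. "The unadjusted model will include indicators of first-stage and second-stage intervention conditions, time of the assessment", plus indicator-by-time terms. In addition, "An additional interaction term of the two intervention indicators will be included". No coding is stated and no model omits the second-stage terms.

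**Aims.** Aim 1 promises a comparison of two frontline interventions and four adaptive strategies. Study Design speaks of three adaptive strategies, meaning the three second-stage arms.

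**The concern.** Being in maintenance is the same thing as having responded. A model that holds second-stage condition fixed at three levels therefore holds response fixed. Its frontline term at weeks 26 and 49 is a contrast within response strata. This is neither the marginal contrast that was sized nor an analysis by random assignment. It is biased for the marginal contrast when response differs by arm and predicts the outcome.

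A response gap is plausible. Response is judged on urine screens in weeks 11 and 12, when the high-intensity arm still receives contingency management. The low-intensity arm does not: "For the last six weeks, they attend weekly group education sessions".

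Three things are at stake:

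- The week-26 and week-49 frontline results. The distortion is roughly the response gap times the responder/non-responder outcome difference, so it is largest for methamphetamine abstinence, which response itself measures.
- Aim 1's strategy comparison. Each strategy mixes responders and non-responders from one frontline arm, and no averaging or weighting step is written.
- Aim 2. The frontline cost-effectiveness ratio counts all later costs, but the plan does not say which analysis supplies the outcome difference in its denominator.

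**Working it through.** **The plan's own figure.** For 60% versus 80%, two-sided 5% (sidedness assumed) and 80% power, pooled-variance formula:

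n = [1.96·√(2·0.7·0.3) + 0.8416·√(0.6·0.4 + 0.8·0.2)]² / 0.20² = 81.2, so 82 per group.

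With 20% attrition, 82/0.8 = 102.5, so 103 against the planned 100. Power at 80 evaluable per group is 79.4%. The stated 20 points reproduces. The open question is whether the model estimates the contrast that was powered.

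**Assumed inputs.** Response 60% (high) and 40% (low). Week-26 abstinence 60% in responders, 20% in Enhanced 1, 30% in Enhanced 2. Randomization 1:1 at both stages. The frontline arm acts only through response.

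*True marginal effect.* High: 0.6×60 + 0.4×25 = 46. Low: 0.4×60 + 0.6×25 = 39. Difference 7.0 points, which is 0.20 × (60 − 25).

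*Three levels.* Responders 60 − 60, Enhanced 1 20 − 20, Enhanced 2 30 − 30. Effect 0.

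*Contrast −1/0/+1, responders at 0.* The contrast averages zero within each arm, so each arm's intercept is its mean. Effect 7.0.

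*Single Enhanced 2 indicator with interaction.*
- At indicator = 0, high: (0.6×60 + 0.2×20)/0.8 = 50.0. Low: (0.4×60 + 0.3×20)/0.7 = 42.9. Difference 7.1.
- At indicator = 1 the difference is 0.
- Averaged over the 25% Enhanced 2 share: 0.75 × 7.1 = 5.4.
- At the pilot's 62% response (72% versus 52%), the difference at indicator = 0 is 53.5 − 47.4 = 6.1. Averaged over the 19% share it is 0.81 × 6.1, about 5.0.

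*Limits of the contrast coding.* If one third of non-responders go to Enhanced 2, it gives 6.98 against a true 7.33. If two thirds do, it gives 6.98 against 6.67. It is exact only on a linear scale with 1:1 re-randomization.

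**Simulation of the planned terms for abstinence.** N = 480 (600 less 20%), 20 clinics of 24, four time points, linear mixed model with clinic and participant intercepts, 400 replicates. Entries are the week-26 frontline estimate in points and the share of trials significant at 5%.

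| Response gap (points) | 0 | 10 | 20 | 30 |
|---|---|---|---|---|
| True effect (exact) | 0 | 3.5 | 7.0 | 10.5 |
| First stage only | −0.3 (6%) | 3.3 (15%) | 7.1 (41%) | 10.5 (73%) |
| Three levels | −0.4 (7%) | −0.1 (8%) | 0.1 (7%) | 0.3 (7%) |
| −1/0/+1 | −0.3 (6%) | 3.3 (15%) | 7.1 (40%) | 10.6 (74%) |
| Single Enhanced 2 indicator | −0.3 (6%) | 3.3 (14%) | 7.1 (40%) | 10.5 (66%) |

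The SD of an estimate is 4.1 to 4.8 points.

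**Sensitivity.**
- *Direct frontline effect of +5 in every stratum, 20-point gap:* true 5 + 7 = 12. Three levels give 5.
- *Low abstinence (25%, 8%, 12%; 17.5% overall):* true 0.20 × (25 − 10) = 3.0. Three levels give 0.
- *Equal 50% response, frontline effect +10 in responders and 0 in non-responders:* marginal 5.0. Three levels give 3.3 averaged equally over levels, 10.0 with maintenance as reference, 0 with an Enhanced reference, and 5.0 averaged by actual shares. Equal response alone is not a safeguard.
- *Viral suppression, 70% in responders and 60% in non-responders, 20-point gap:* true 0.20 × 10 = 2.0. Three levels give 0. With 75% and 55%, true 4.0 against 0. The standard error for two groups of 80 near 65% is √(2 × 0.65 × 0.35/80) = 7.5 points.

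**Week 13.** In a separate large simulated sample (response 72% versus 52%; abstinence 80% and 20% by response at week 13, 60% and 20% later), the raw differences were 11.3 points at week 13 and 7.1 at week 26. Three levels fixed over time gave −0.8 and −0.9. Three levels active only after week 13 gave 11.3 and −1.3.

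**The case against.** The strongest reply is that the harmful reading fits the wording less well. The plan speaks of one interaction term between two indicators, whereas three levels would need two second-stage indicators and two interaction terms. With a single Enhanced 2 indicator, or −1/0/+1, the simulated estimate nearly matches the first-stage-only analysis. This is a fair reading, but the same paragraph refers to second-stage conditions in the plural, there are three of them, and one binary indicator cannot represent three. A single indicator also gives 7.1 or 5.4 from the same fit, depending on where the effect is read.

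The intent-to-treat sentence and the inclusion of all later costs suggest that a marginal effect was intended. That is likely, but neither sentence removes a term or names a model. The pooling sentence under Sample size determination concerns second-stage comparisons.

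Several points stand:

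- The illustrated abstinence rates are high beside the plan's 80% to 90% base rate for substance use. At about 17.5% abstinence the loss is 3 points, not 7.
- The viral suppression distortion is small against its standard error and the 20-point design difference. HIV risk behaviors were not quantified.
- If time-varying means that second-stage terms start after week 13, the week-13 contrast is sound.
- The planned model, coded as three levels or −1/0/+1, can already compare Enhanced 1 with Enhanced 2, so a separate analysis there is an improvement in clarity. Strategy means could be built from cell means, and Figure 1, which is not shown, may draw the strategies. No such step is written, and without a first-by-second-by-time term the cell means are constrained over time.

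**Conclusion.** The concern holds. The only effectiveness model contains a term that, for maintenance, is response itself. Its coding is not given, and no analysis of the first-stage contrast without that term is specified. Under three-level coding the week-26 and week-49 frontline effect loses everything that acts through response: 7.0 points of abstinence in the main scenario, 3.0 at lower abstinence rates, and about 2 to 4 points for viral suppression, all at a 20-point response gap. These sizes rest on assumed response and outcome rates. The loss disappears under −1/0/+1 coding with 1:1 re-randomization on a linear scale, or if response neither differs by arm nor marks strata with different frontline effects. Even the correct analysis of a 7-point effect was significant in only 41% of simulated trials, so the main fault is a wrong or undefined target, with lost power second. Separately, the text does not say how Aim 1's four strategies are estimated. Because the trial is open label and data managers know the assignments, these choices should be fixed before outcomes are analyzed.

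**What to change.** Pre-specify three analyses.

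1. **Frontline effect at weeks 13, 26 and 49.** All randomized participants; first-stage arm, time, arm-by-time, HIV status, clinic and participant random effects; no second-stage terms. For binary outcomes report standardized (marginal) risk differences, to match the sample-size statement. Label the later effects as including the trial's second-stage mix.
2. **Enhanced 1 versus Enhanced 2.** Re-randomized non-responders only, adjusted for first-stage arm and HIV status, with the same random effects.
3. **Four embedded strategies.** Define them in text and reconcile the terms three and four adaptive strategies. Estimate them by inverse-probability weighting with replication of responders (weights 1/(1/2) = 2 for responders and 1/(1/2 × 1/2) = 4 for non-responders if both stages are 1:1, which the protocol should state). Alternatively, standardize cell means over arm-specific response rates. Standard errors must allow for replication within participant and for clustering in 20 clinics.

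State that the frontline cost-effectiveness ratio uses the outcome difference from analysis 1 and that the strategy ratios use analysis 3. If the present model is kept as secondary, give the second-stage coding and say that second-stage terms apply only after week 13.

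The cost is analysis-plan wording and some programming, with no new participants or data. Strategy estimates will have slightly wider standard errors.
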